8 STUDY TERMINATION

8.1 Subject Discontinuation

A subject may voluntarily withdraw or be withdrawn from the study by the Investigator at any time for reasons including, but not limited to, the following:

- The subject wishes to withdraw from further participation.
- A serious or life-threatening AE occurs or the Investigator considers that it is necessary to discontinue study drug to protect the safety of the subject.
- The subject deviated from the protocol.
- The subject's behavior is likely to undermine the validity of his/her results.
- The subject becomes pregnant

If a subject is discontinued prematurely, the Investigator must provide an explanation in the CRF (Investigator's Comment Log) and complete the End of Study Record for that subject. If study drug has been administered, the Investigator should make every effort to perform all scheduled evaluations prior to discharge. In the event that a subject discontinues prematurely due to an AE, the subject will be followed until the Investigator determines the AE has resolved, the AE is no longer considered clinically significant, the subject is lost to follow-up, or for 30 days following discontinuation of UT-15C.

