⁴ **Visit windows** are ± 1 month from the scheduled number of months from first exposure to UT-15C SR, except for Visit 1, which is ± 2 weeks.

⁵ **VISIT 1** – Only for subjects randomized to placebo in TDE-PH-301, 302, or 308; 3 months after subject's first exposure to UT-15C. Also applies to subjects enrolled from the TDE-PH-202 study who are beginning a dose of 0.25mg BID.

VISIT 2 – 6 months after subject's first exposure to UT-15C SR.

VISIT 3 – 12 months after subject's first exposure to UT-15C SR.

VISIT 4 – 24 months after subject's first exposure to UT-15C SR.

VISIT 5 – 36 months after subject's first exposure to UT-15C SR.

⁶ **Weekly telephone call** required for 4 weeks for all subjects who transition from a BID to TID regimen to assess dose titration needs, potential adverse events, concomitant medication usage and PAH signs and symptoms.

⁷ **Monthly telephone calls** (at a minimum) required for all subjects participating in TDE-PH-304 to assess dose titration needs, potential adverse events, concomitant medication usage and PAH signs and symptoms.

⁸ **Visits beyond Visit 5** will occur yearly until either the drug receives regulatory approval in a particular region or the sponsor discontinues the study. Assessments after visit 5 will include adverse events, PAH concomitant medications, concomitant medications, clinical laboratories, and compliance/drug accountability.

⁹ **EXIT** – If the subject discontinues from the study between scheduled visits, every effort should be made to obtain the exit assessments just prior to termination from the study.

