9 ADVERSE EVENT REPORTING

9.1 Definitions

9.1.1 Adverse Event

An AE is any untoward medical experience occurring to a subject during a clinical trial whether or not it is related to the study drug. An AE may include an intercurrent illness, injury, or any other concomitant impairment of the subject's health, as well as abnormal laboratory findings if deemed to have clinical significance. AEs may also include worsening of an existing symptom or condition or post-treatment events that occur as a result of protocol-mandated procedures.

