9.1.2 Serious Adverse Event

A serious adverse event (SAE) is an AE occurring at any dose that results in any of the following outcomes:

- Death
- A life-threatening AE
- Inpatient hospitalization or prolongation of existing hospitalization
 - Planned hospitalizations (e.g., admission for elective surgery or right heart catheterization) do not qualify as SAE's
- A persistent or significant disability/incapacity
- A congenital anomaly/birth defect

In addition, important medical events that may not result in death, be life-threatening, or require hospitalization may be considered serious when, based upon appropriate medical judgment, they may jeopardize the subject and require medical/surgical intervention to prevent one of the outcomes listed above. Examples of such medical events include allergic bronchospasm requiring intensive treatment in an emergency room or at home, blood dyscrasias or convulsions that do not result in hospitalization, or the development of drug dependency or drug abuse.

Life-threatening means that the subject was, in the view of the Investigator, at immediate risk of death from the event as it occurred. It does not mean that the event, had it occurred in a more severe form, might have caused death.

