9.2 Documentation of Adverse Events

An AE or SAE occurring during the study must be documented in the subject's source documents and on the appropriate CRF page. Information relating to the AE such as onset and cessation date and times, intensity, seriousness, relationship to study drug, and outcome will also be documented in the CRF (see Appendix C for definitions). Where possible, AEs should be recorded using standard medical terminology. If several signs or symptoms are clearly related to a medically defined diagnosis or syndrome, the diagnosis or syndrome should be recorded on the CRF page, not the individual signs and symptoms.

All adverse events should be followed until resolution (or return to normal or baseline values), until they are judged by the Investigator to no longer be clinically significant, or for 30 days following discontinuation of UT-15C. All SAEs that occur during the study will be followed until resolution, death, or the subject is lost to follow-up. Supplemental measurements and/or evaluations may be necessary to fully investigate the nature and/or causality of an AE or SAE. This may include additional laboratory tests, diagnostic procedures, or consultation with other healthcare professionals. CRF pages should be updated with any new or additional information as appropriate.

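### Protocol 8.1 and 9.2 give different follow-up end points for an SAE that ends treatment, and the available text sets no general window for events starting after exit

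*Protocol*

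**What the plan says.** Protocol 8.1 names among its reasons for withdrawal: "A serious or life-threatening AE occurs or the Investigator considers that it is necessary to discontinue study drug". For subjects who leave for that kind of reason it then sets the follow-up rule: "In the event that a subject discontinues prematurely due to an AE, the subject will be followed until the Investigator determines the AE has resolved". Alternatives follow: the event has lost clinical significance, or "the subject is lost to follow-up, or for 30 days following discontinuation of UT-15C".

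Protocol 9.2 first gives a rule for adverse events in general, with the same kind of exits: "until they are judged by the Investigator to no longer be clinically significant, or for 30 days following discontinuation of UT-15C". Its next sentence deals with serious events alone: "All SAEs that occur during the study will be followed until resolution, death, or the subject is lost to follow-up".

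On new events, Protocol 9.2 requires documentation of those occurring during the study. The last planned assessment is the exit visit. For a subject who leaves between visits, footnote 9 of Table 3.2 says that "every effort should be made to obtain the exit assessments just prior to termination from the study". The monthly calls in Protocol 7.1 are for subjects still actively participating. The adverse event definition in Protocol 9.1.1 reaches beyond treatment only for "post-treatment events that occur as a result of protocol-mandated procedures".

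SAP 11.4 lists and summarises deaths within 30 days of study participation. SAP 11.2 defines treatment-emergent events without a closing date, and also reports events per patient-year. SAP 11.1 defines exposure as time on active drug.

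**The concern.** Long-term safety is one of the stated objectives, and the SAEs that end treatment are among the events whose outcome matters most to it. If 8.1 is the section a site opens when a subject stops, an unresolved SAE may be closed at day 30, or sooner if judged no longer clinically significant. A site working from 9.2 would keep following the same event. Outcome data for these SAEs would then depend on which section the site read.

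The second issue is related but separate. The 30-day periods in 8.1 and 9.2 concern events that already exist. They do not say whether an event that begins after exit is to be sought or reported. SAP 11.4 nevertheless expects to count deaths over a 30-day period, and the protocol schedules no contact in that period through which a site would learn of one. Ascertainment would then rest on local practice.

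**Working it through.** No formula applies, and the plan states no figure to reproduce. The check compares the rules.

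**Does 8.1 apply to SAEs?** Yes. Protocol 9.1.2 makes an SAE a kind of AE: "A serious adverse event (SAE) is an AE occurring at any dose that results in any of the following outcomes". Section 8.1 itself lists a serious event as a reason for withdrawal, and its follow-up sentence makes no exception for one.

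**Does the SAE sentence in 9.2 apply to the same event?** Yes. It covers all SAEs during the study, and an SAE that causes discontinuation began while the subject was participating.

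**Where do the two sections differ?**

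| State of an SAE that ended treatment | 8.1 | 9.2, SAE sentence |
|---|---|---|
| Resolved before day 30 | may end | may end |
| Subject lost before day 30 | may end | may end |
| Unresolved, judged no longer clinically significant | may end | continues |
| Unresolved at day 30 after stopping drug | may end | continues |

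The first two rows agree and the last two do not. Section 8.1 joins its end points with a plain alternative and does not say whether the earliest or the latest governs. On the ordinary reading, any one of them suffices.

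**What reaches past the last dose or past exit?**

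- Events between last dose and exit: covered, because collection runs for the duration of the study and does not stop at the last dose.
- AEs and SAEs already present at exit: followed under 8.1 and 9.2, whatever the reason for leaving.
- Post-treatment events caused by study procedures: within the definition in 9.1.1.
- Pregnancy: followed each trimester under 9.5, with abnormal outcomes becoming AEs or SAEs.
- Deaths within 30 days of participation: counted by SAP 11.4, with no scheduled protocol contact to find them.
- Any other AE or SAE with onset after exit: no window stated in the available text. Protocol 9.3 sets a 24-hour clock from awareness but no period during which sites must look.

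**Do the SAP pieces fit together?** The 30 days in Protocol 8.1 and 9.2 run from stopping the drug, whereas those in SAP 11.4 run from study participation. The two anchors differ whenever last dose and exit fall on different days. In SAP 11.2 the treatment-emergent numerator has no closing date, while the patient-year denominator stops with active drug. Post-exposure events would therefore enter the rate without any matching time.

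**The case against.** The strongest reply is that 8.1 merely repeats the general AE rule and that 9.2, by moving from all AEs to all SAEs in consecutive sentences, supplies the specific rule. A site that follows an SAE to resolution satisfies both sections, so none is forced into a breach. Protocol 9.3 also asks for updated SAE reports within 48 hours of new information, with no end date. This softens the conflict considerably. It does not remove it, because 8.1 is equally specific to discontinuation caused by an AE and neither exempts SAEs nor points to 9.2. The 48-hour rule governs information once received and does not require anyone to seek it.

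On events after exit, a reader might infer that nothing arising off drug is captured. The documents do not support that. Collection continues to exit, ongoing events are followed, and pregnancy outcomes, procedure-related events and 30-day deaths each have a provision. Protocol 3.3.2.2 also adopts the parent protocols' AE reporting instructions and refers to Appendix C. Neither was in the available text, and an onset window could sit in either.

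It is also fair to object that extending the treatment-emergent window carelessly would inflate events per patient-year. That objection stands, and the fix has to deal with it.

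**Conclusion.** The point holds in a limited form. For an SAE that ends treatment and is not resolved, 8.1 allows follow-up to stop at 30 days or on loss of clinical significance, and 9.2 allows neither. The passages must be reconciled; this review does not say which end point is right. Separately, the available text schedules no contact after exit and gives no general onset window for new AEs or SAEs, while SAP 11.4 reports deaths over a period that extends past participation. This second part is conditional on Appendix C and the parent-study instructions not already supplying such a window.

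The size cannot be given as a number of events. A reader might multiply planned enrolment by 30 days and an SAE rate to count lost events, but the documents give no post-exit SAE rate. Subjects who die on treatment contribute no such time, some subjects are already under follow-up for ongoing events, and the text does not say that everyone is off drug once the study closes. What can be said is that the conflict applies to any subject whose SAE ends treatment without resolving, and the missing window to each subject who exits alive, out of about 900 planned plus any from additional protocols. Correcting it is worthwhile because it is cheap and bears on a stated objective.

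**What to change.** 1. Reconcile Protocol 8.1 with 9.2 so that a single follow-up end point applies to SAEs leading to discontinuation, and add a cross-reference in 8.1.
2. Check Appendix C and the parent-study instructions for an onset window. If there is none, add one closing telephone contact about 30 days after exit for every exiting subject, whatever the reason, to record deaths and new AEs or SAEs. State the window in 9.2 and 9.3. This collects the data that SAP 11.4 relies on.
3. In SAP 11.2, use the same window and the same anchor as 11.4, with that anchor stated explicitly. Keep events after the end of exposure out of the events-per-patient-year numerator, or add the matching time to the denominator.

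The cost is a few sentences in the protocol and SAP and one call per exiting subject: about 900 × 1 = 900 calls at most for the planned enrolment, fewer where subjects die before the call falls due. The SAE count would rise slightly. No dose or treatment rule changes.

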8.2 Study Discontinuation

The study may be stopped at any time if, in the opinion of the Investigator and/or sponsor, continuation of the study represents a serious medical risk to the subjects. This may include, but is not limited to, the presence of serious, life-threatening, or fatal adverse events or adverse events that are unacceptable in nature, severity, or frequency. The sponsor reserves the right to discontinue the study for any reason at any time. In the event the sponsor discontinues the study, an EXIT visit for each subject should be scheduled.

8.3 Site Discontinuation

The study may also be terminated at a given center if:

- The Principal Investigator elects to discontinue the study
- The Sponsor elects to discontinue the study at the site
- U.S. FDA, European, or national regulations are not observed
- The protocol is violated
- Changes in personnel or facilities adversely affect performance of the study

9 ADVERSE EVENT REPORTING

9.1 Definitions

9.1.1 Adverse Event

An AE is any untoward medical experience occurring to a subject during a clinical trial whether or not it is related to the study drug. An AE may include an intercurrent illness, injury, or any other concomitant impairment of the subject's health, as well as abnormal laboratory findings if deemed to have clinical significance. AEs may also include worsening of an existing symptom or condition or post-treatment events that occur as a result of protocol-mandated procedures.

9.1.2 Serious Adverse Event

A serious adverse event (SAE) is an AE occurring at any dose that results in any of the following outcomes:

- Death
- A life-threatening AE
- Inpatient hospitalization or prolongation of existing hospitalization
 - Planned hospitalizations (e.g., admission for elective surgery or right heart catheterization) do not qualify as SAE's
- A persistent or significant disability/incapacity
- A congenital anomaly/birth defect

In addition, important medical events that may not result in death, be life-threatening, or require hospitalization may be considered serious when, based upon appropriate medical judgment, they may jeopardize the subject and require medical/surgical intervention to prevent one of the outcomes listed above. Examples of such medical events include allergic bronchospasm requiring intensive treatment in an emergency room or at home, blood dyscrasias or convulsions that do not result in hospitalization, or the development of drug dependency or drug abuse.

Life-threatening means that the subject was, in the view of the Investigator, at immediate risk of death from the event as it occurred. It does not mean that the event, had it occurred in a more severe form, might have caused death.

9.1.3 Expected Adverse Event

Adverse events associated with progression of PAH:

An expected event that is related to the progression of a subject's PAH is defined in Appendix D, Part A. All events that occur during the course of the study that are included on this list and felt to be related to progression of disease by the Investigator should NOT be recorded as AEs in the CRF as the most relevant PAH symptoms will be evaluated and recorded as an efficacy endpoint and all other events will be captured as disease related events. If the event is either serious or unusual with respect to intensity, frequency, or duration, OR there is a reasonable possibility that it may have been caused by study drug, it must be recorded as an AE in the CRF.

Adverse events known to be associated with treprostinil therapy:

An expected AE for UT-15C is defined as any AE that is defined in terms of nature, severity, or frequency in the current Investigators' Brochure and in Appendix D, Part B. When an adverse event may be attributed to the progression of pulmonary hypertension or UT-15C SR (e.g., listed in both Parts A and B) it must be recorded as an AE in the CRF if the event is either serious or unusual with respect to intensity, frequency, or duration, OR there is a reasonable possibility that it may have been caused by study drug.

Expected events attributable to UT-15C (e.g., listed in Part B only) must always be recorded as AEs in the CRF.

If an event listed in Appendix D Part A or B occurs during the conduct of the trial, it will not give rise to submission of an expedited safety report despite being considered serious and possibly attributable to the study drug, unless the United Therapeutics Medical Monitor, responsible for assessing the case considers it to be unusual (e.g., more severe than expected) and therefore reportable. The data regarding such events will always be recorded in the clinical study database, regardless of reportability.

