2.2 Study Endpoints

The safety endpoints are as follows:

- Adverse events
- Clinical laboratory parameters

PAH concomitant medications also will be documented.

Efficacy will be assessed by a 6-Minute Walk Test and Borg Dyspnea Score to be conducted after each subject has completed one year of therapy with UT-15C SR.

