7 EXPERIMENTAL PROCEDURES

7.1 Open-Label Phase

All values collected at the subject's respective final visit in protocol TDE-PH-202 TDE-PH-203, TDE-PH-205, TDE-PH-301 or TDE-PH-308 and TDE-PH-302 will serve as the baseline assessments for the open-label study.

Subjects receiving placebo in the previous study must be contacted weekly by telephone (at a minimum) during the first 12 weeks of the open-label study and, if necessary, brought in for clinic visits in the first several months of the study to ensure subject safety. This also applies to subjects enrolled from the TDE-PH-202 study (Dose Groups 1 or 2) who are beginning a dose of 0.25mg BID.

Monthly telephone calls (at a minimum) must be conducted for all subjects actively participating in the open-label study, regardless of study drug allocation (UT-15C SR or placebo) in the previous study.

In addition to the scheduled study visits, as listed below, all subjects must be seen in the clinic no less than once every six months for routine standard of care medical evaluation.

Weekly telephone calls (required Weeks 1-12; only for subjects randomized to placebo in previous study). This also applies to subjects enrolled from the TDE-PH-202 study (Dose Groups 1 or 2) who are beginning a dose of 0.25mg BID.

- Adverse events
- PAH concomitant medications
- Concomitant medications

Drug accountability / compliance

Weekly telephone calls (required for 4 weeks for subjects who transition from BID to TID dosing)

- Adverse Events
- PAH concomitant medications
- Concomitant medications
- Drug accountability/compliance

Monthly telephone calls (required for all subjects participating in open-label study)

- Adverse events
- PAH concomitant medications
- Concomitant medications
- Drug accountability / compliance

Visit 1 (three months after first dose of UT-15C SR; only for subjects randomized to placebo in previous study). This also applies to subjects enrolled from the TDE-PH-202 study (Dose Groups 1 or 2) who are beginning a dose of 0.25mg BID.

- Adverse events
- PAH concomitant medications
- Concomitant medications
- Clinical laboratories
- Drug accountability/compliance

Visit 2 (six months after first dose of UT-15C SR)

- Adverse events
- PAH concomitant medications
- Concomitant medications
- Clinical laboratories
- Drug accountability/compliance

Visit 3 (12 months after first dose of UT-15C SR)

- Adverse events
- PAH concomitant medications
- Concomitant medications
- Clinical laboratories

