## 10.2 CLINICAL EVENTS

Clinical events, including death, study discontinuation for any reason, addition of PAH therapy, and addition of parenteral PAH therapy, will be listed, including date of each event, if applicable, as well as the subject's previous background therapy status (naïve, single background therapy, or double background therapy). Note that events may have occurred during the parent study for those subjects treated with active drug during the parent study, thus event data from the parent study will be included in these data analyses. The following combinations of clinical events will be utilized for summarization and plotting purposes, separately:

- Study discontinuation for any reason
- Death or discontinuation due to disease progression
- Death, discontinuation due to disease progression or addition of PAH therapy
- Death, discontinuation due to disease progression or addition of parenteral PAH therapy
- Death

Summary tables will be produced by previous study and overall and will display the number (percent) of subjects who experienced each event combination detailed above. Kaplan-Meier (K-M) curves for the above combinations of clinical events will be provided separately. Each K-M plot will include a time to clinical event curve for each of the previous studies overlaid on the same plot.

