## 11.3 DISEASE RELATED EVENTS

The disease-related events reported during the TDE-PH-304 study will be listed, including subject number, previous study, and symptom. The summary will include the number (percent) of subjects who reported each symptom by previous study and overall.

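### Protocol 9.1.3 sends the main PAH progression symptoms to an efficacy endpoint this study lacks, and the remaining record is unscheduled and covers a different on-drug period from the AE tables

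*Protocol*

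**What the plan says.** Protocol 9.1.3 instructs sites not to enter Appendix D Part A events as AEs when the investigator attributes them to disease progression. It names two destinations instead. The first is that "the most relevant PAH symptoms will be evaluated and recorded as an efficacy endpoint"; the second, for every remaining event, is a disease-related-event record. An exception returns an event to the AE record: "If the event is either serious or unusual with respect to intensity, frequency, or duration", or if the drug may reasonably have caused it.

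On endpoints, Protocol 2.2 states "Efficacy will be assessed by a 6-Minute Walk Test and Borg Dyspnea Score", done after one year of therapy. SAP 2.2 says the same. The only other efficacy analysis is SAP 10.2: "Clinical events, including death, study discontinuation for any reason, addition of PAH therapy, and addition of parenteral PAH therapy, will be listed".

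On collection, Table 3.2 footnotes 3, 6 and 7 require the weekly and monthly calls "to assess dose titration needs, potential adverse events, concomitant medication usage and PAH signs and symptoms". Section 7.1 has its own content list for each call type, for example under "Monthly telephone calls (required for all subjects participating in open-label study".

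On analysis, SAP 11.3 states "The disease-related events reported during the TDE-PH-304 study will be listed", with a count of subjects per symptom. SAP 11.2 treats parent-study AEs as treatment-emergent for subjects who received active drug there, and SAP 11.1 counts their parent-study exposure.

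**The concern.** Protocol 9.1.1 allows worsening of an existing symptom to be an AE, so the rule in 9.1.3 removes events that would otherwise be counted. That is acceptable if each removed event has another defined place, a scheduled moment of collection and a matching analysis window. Here one of the two named places does not exist, the other is not scheduled, and its table covers a different period from the AE table.

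Long-term safety is a stated objective, and there is no control arm against which a shortfall in recorded worsening would show up. If sites apply 9.1.3 differently, the symptom counts in SAP 11.3 will partly reflect site practice. A reader who sets the AE table beside the disease-related-event table would also assume that both describe the same time on drug.

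**Working it through.** The plan gives no figure on this point, so the check is mainly a comparison of the texts.

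**Step 1. Where 9.1.3 sends each Part A event judged to be progression**

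| Event | Destination in 9.1.3 | Does it exist in this study? |
|---|---|---|
| Serious, unusual or possibly drug-caused | AE record | Yes (SAP 11.2) |
| None of these, and among the most relevant symptoms | Efficacy endpoint | No symptom endpoint |
| None of these, any other | Disease-related events | Yes (SAP 11.3, Table 14.3.1.8, Listing 16.2.7.3) |

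**Step 2. Is there a symptom endpoint under another name?** Protocol 2.2 and SAP 2.2 name two efficacy measures, the walk test and the Borg score. Borg rates one symptom, dyspnea, once, at Visit 3 (Protocol 3.3.1). SAP 10.2 covers death, discontinuation and added therapy. The efficacy tables in SAP 12.2 are walk, Borg and clinical-event tables. None is a PAH signs-and-symptoms assessment, so the second row of Step 1 has no destination. The text supplied does not say which symptoms count as most relevant.

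**Step 3. Is the remaining record scheduled?** Table 3.2 has six assessment rows: AEs, PAH concomitant medications, concomitant medications, walk/Borg, laboratory parameters and drug accountability. None is disease-related events or PAH symptoms. The Section 7.1 visit lists add nothing.

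| Call content | Table 3.2 footnotes 3, 6, 7 | Section 7.1 call lists |
|---|---|---|
| Adverse events | Yes | Yes |
| Concomitant medications | Yes | Yes (PAH and other) |
| Titration needs | Yes | No |
| PAH signs and symptoms | Yes | No |
| Drug accountability/compliance | No | Yes |

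The calls must therefore ask about symptoms under one section, while the matching list in another omits them. Neither names the form on which the answer is recorded.

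**Step 4. Analysis windows for subjects on active drug in the parent study**

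| SAP section | Parent-study period included? |
|---|---|
| 10.2 Clinical events | Yes |
| 11.1 Exposure | Yes |
| 11.2 AEs | Yes |
| 11.3 Disease-related events | No, TDE-PH-304 only |
| 11.5 Laboratory tests | Yes |

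Section 11.3 is the only one of the five that stops at entry to TDE-PH-304, and the SAP gives no reason.

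**Step 5. How long is the uncovered period?** The share of on-drug time outside SAP 11.3 is (parent-study weeks on active drug) / (total weeks on active drug). The only parent duration in the documents is the 12-week Treatment Phase of TDE-PH-202. For a subject who completed it on drug:

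- over the first on-drug year: 12 / 52 = 23%
- over 36 months (156 weeks): 12 / 156 = 8%
- for a former placebo subject: 0%

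These are shares of time for one parent study, not shares of events. They cannot be carried over to the other parent studies.

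**The case against.** The strongest reply is that nothing is lost. If there is no symptom endpoint, the sensible reading of 9.1.3 is that every non-AE Part A event falls into the disease-related group, which SAP 11.3 lists and tabulates by symptom. Section 9.1.3 also ends by saying that data on such events always reach the study database. Sites must ask about symptoms on the calls, so the Section 7.1 lists are incomplete but do not contradict the footnotes. Clinically important worsening appears elsewhere: SAP 10.2 reports death, discontinuation for progression and added therapy, with the parent period included; SAP 11.1 tabulates progression of PAH as a status at each visit; SAP 9.3.3 summarizes added PAH medication. Recording expected progression apart from AEs is a legitimate design choice.

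Much of this stands. A reader might infer that the study collects no symptoms, that all progression events leave the AE tables, or that worsening is under-reported. The documents support none of these. Borg and the calls cover symptoms; serious, unusual and possibly drug-caused events remain AEs; and a disease-related-event table is planned. A reader might also infer that parent-study progression symptoms appear in no table. Protocol 3.3.2.2 carries the parent studies' AE instructions into this one, which suggests the same exclusion applied there, but the documents do not say where the parent studies stored these events.

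The reply does not remove the defect. The sensible reading asks sites to disregard a clause of the rule. The database assurance sits in a paragraph on expedited reporting and names no form. SAP 10.2, 11.1 and 9.3.3 do not capture non-serious symptoms that lead to no change of therapy or status. None of this explains the window in SAP 11.3.

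**Conclusion.** The point holds as a defect of specification and should be corrected. Protocol 9.1.3 relies on a PAH-symptom efficacy endpoint that the study does not have. Non-serious progression symptoms therefore depend on one record, whose literal scope leaves out the most relevant symptoms and which no schedule mentions. Separately, the AE and disease-related-event tables cover different on-drug periods for every subject who was on active drug in the parent study.

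The size in events is unknown. The time shares in the working illustrate the window mismatch for TDE-PH-202 only.

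The conclusion rests on the protocol and SAP text. Appendix D, the CRF and the parent protocols were not available, and their absence is not held against the plan. If the CRF already has a disease-related-event page completed at every contact for all Part A events, the recording gap is one of wording only; the window mismatch would remain.

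**What to change.** - **Protocol 9.1.3:** delete the efficacy-endpoint clause and state that every Part A event not recorded as an AE goes on the disease-related-event CRF page.
- **Protocol Table 3.2 and Section 7.1:** add disease-related events as an item at visits and calls, and reconcile the Section 7.1 call lists with the Table 3.2 footnotes on PAH signs and symptoms and on titration needs.
- **SAP 11.3:** for subjects on active drug in the parent study, include parent-study disease-related events where these were collected, to match SAP 11.2. If they were not collected, or are left out on purpose, label Table 14.3.1.8 and Listing 16.2.7.3 as covering TDE-PH-304 only and say why.

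The cost is one protocol sentence, aligned lists, one SAP line and some programming. Disease-related-event counts will rise; the report should explain that this reflects wider capture and, where parent-study data are added, a longer window.
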